1. EXECUTIVE SUMMARY

Title:	Diuretic Optimal Strategy Evaluation in Acute Heart Failure: the DOSE-AHF study				
Indication:	Acute heart failure				
Location:	Regional clinical centers and associated hospitals in United States and Canada.				
Rationale	Although most patients admitted with AHF receive IV furosemide treatment, little data exist to guide dosing or route of administration. Observational data suggest little relationship between dose and efficacy, and the possibility of dose related adverse effects on renal function and mortality.				
Objectives:	To evaluate the safety and efficacy of				
	High intensification diuretic strategy vs. low intensification diuretic strategy in AHF				
	IV continuous infusion vs. intermittent IV bolus Q12 hours				
Study Design:	300 patient randomized, controlled, multicenter clinical trial using a 2 x 2 factorial design				
Treatment	High intensification (2.5 x oral dose) IV furosemide by Q12 hours bolus				
Regimens:	High intensification (2.5 x oral dose) IV furosemide by continuous infusion				
	Low intensification (1 x oral dose) IV furosemide by Q12 hours bolus				
	Low intensification (1 x oral dose) IV furosemide by continuous infusion				
Primary Endpoints:	Safety: Change in serum creatinine from randomization to 72 hours				
Enupoints.	Efficacy: Patient global well being assessment by Visual Analog Scale (VAS) area under the curve for 72 hours				
Secondary	Change in weight				
Endpoints:	Freedom from congestion at 72 hours				
	Change in bivariate vector of creatinine and weight at 72 hours				
	 Differences in Dyspnea VAS AUC over 24, 48 and 72 hours Differences in PGA VAS AUC over 24 and 48 hours 				
	Change in Creatinine at 24, 48, 96 hours, day 7 (or discharge) and 60 days				
	Change in Cystatin C at 72 hours, Day 7 (or discharge) and 60 days				
	Persistent/Worsening Heart Failure				
	Development of cardio-renal syndrome (CRS)				
	Treatment Failure				
	Net fluid loss over 72 hours				
	Time from randomization to discharge of index hospitalization				
	Days hospitalized for heart failure or deceased in 60 days from randomization				

1.1 Study Flow Chart

2. HYPOTHESES AND OBJECTIVES

2.1 Primary Hypotheses: Dose Intensification

The primary hypotheses to be tested in the "high intensification" vs. "low intensification" comparison are:

- That a low intensification strategy causes less renal dysfunction than a "high intensification strategy, as measured by change in serum creatinine from randomization to 72 hours
- That a "low intensification" strategy is more efficacious in relieving acute symptoms compared to "high intensification" strategy, as measured by the area under the curve of serial visual analog assessments for global well being over 72 hours

2.2 Primary Hypotheses: Route of administration

The primary efficacy hypotheses to be tested in the continuous infusion vs. intermittent bolus comparison are:

- That continuous IV infusion of furosemide causes less renal dysfunction than twice daily IV bolus administration, as measured by change in creatinine from baseline to 72 hours
- That continuous IV infusion of furosemide is more efficacious at relieving acute symptoms compared to twice daily bolus administration, as measured by the area under the curve of serial visual analog assessments for global well being over 72 hours

These hypotheses will be evaluated in the context of a randomized controlled clinical trial using a 2 x 2 factorial design. Each factor (main effect) in the design will be tested at the α =0.025 level.

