11. OUTCOME DETERMINATIONS

11.1 **Primary Endpoints**

This study will use co-primary endpoints

• Change in serum creatinine from randomization to 72 hours

• Area under the Curve (AUC) for Patient Global Assessment by VAS over 72 hours

Rationale for Primary Endpoints:

Change in creatinine from randomization to 72 hours was chosen as the primary safety endpoint due to the observed association between diuretic dosage and worsening renal function and the known association of worsening renal function with other adverse outcomes.

For the assessment of short term efficacy, a variety of endpoints have been utilized in prior AHF studies. These include patient self assessments of symptoms, typically either dyspnea or global well being (termed patient global assessment (PGA)). These self assessments are usually performed using a visual analog scale (VAS) or Likert scale. The DOSE-AHF study will use the PGA by VAS over 72 hours as the primary endpoint for efficacy. The rationale for this choice is that although dyspnea is the primary symptom for most patients with AHF, other symptoms (fatigue, edema, etc) may also be important and should be captured in the primary efficacy endpoint. We have chosen a patient symptom assessment r ather than other measures of diuretic efficacy such as weight change or urine output, because while these measures capture the pharmacodynamic effects of diuretic therapy, they may not be tightly correlated with other clinical events (such as rehospitalization or death), and are therefore not ideal surrogates in the assessment of efficacy.

Patients will be asked to self assess both their general well being and their level of dyspnea using a visual analog scale (VAS) method. For PGA, patients will mark their global well being on a 10 cm vertical line, with the top labeled "best you have ever felt" and the bottom labeled "worst you have ever felt". For dyspnea, the labels will be "I am not breathless at all" and "I am as breathless I have ever been". The VAS is scored from 0 to 100 but the patient is unaware of the numerical value of their response. Patients will self assess both PGA and dyspnea at randomization, 6, 12, 24, 48, 72, and 96 hours. The area under the curve for PGA assessment over the first 72 hours will be the primary efficacy endpoint (AUC for PGA VAS).

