14. STATISTICAL CONSIDERATIONS

14.1 Overview

Means, standard deviations, medians, 25th and 75th percentiles will be presented for continuous variables; the number and frequency of patients in each category will be presented for nominal variables. Statistical tests with a p value < 0.05 will be considered statistically significant, unless otherwise stated. Analyses will be performed using SAS software (SAS Institute, Inc, Cary, NC).

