14.2 Analysis of Primary Endpoints

The primary analysis will be made on an intention-to-treat basis, with patients allocated to the treatment to which randomized. General linear models will be used to examine the effect of each of the main effects on the two co-primary outcomes. The dependent variables in the regression model will be the change in creatinine value from baseline to 72 hours and the AUC for the PGA VAS from baseline through 72 hours. Independent variables in the model will include the main effects of furosemide dose and mode of administration, and the baseline creatinine level. An interaction term will be included if the p-value for that parameter estimate is less than 0.025. For each co-primary outcome, the two main effects will be that the treatment (either dose or mode of administration) has no effect on either of the co-primary outcomes.

We anticipate that some patients may die before all scheduled post-baseline creatinine values can be taken, and that these losses will introduce bias into the main effects comparisons. For the primary analyses, the values imputed will be 0 for the PGA VAS after the time of death and the highest post-baseline creatinine measurement. Sensitivity analyses, including analysis of only complete cases and imputing the worst creatinine value for deaths, will be employed to assess the degree to which these missing values impact the results.

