14.3 Sample Size

For purposes of power calculations, we have applied a Bonferroni adjustment to the alpha level (0.05/2 = 0.025) to allow for two co-primary endpoints. We assume that the effect of both dose and administration mode will be additive (i.e. no interaction). In our sample size calculations shown below we assess the sensitivity of the power to subadditivity of the main effects. Due to the short-term nature of the study, missing data due to loss-to-followup are expected to be rare. In addition, because this study design is testing initial treatment strategies, we do not anticipate problems with adherence to the protocol guidelines.

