14.3.1 Change in Creatinine at 72 hours

The standard deviation observed for the change in creatinine from baseline to discharge in the ESCAPE trial (unpublished data) was 0.47 mg/dL. Similarly, in the control arm of the UNLOAD study (unpublished data), the standard deviation of the change in creatinine from baseline to discharge was 0.5 mg/dL. With 300 patients, we will have approximately 88% power to detect a difference in mean creatinine of 0.20 mg/dL for each main comparison, assuming a standard deviation of 0.5 mg/dL. Assuming a smaller standard deviation of 0.4 mg/dL, we would have approximately 98% power to detect a difference of 0.2 mg/dL. The effect of various standard deviations on the power to detect given mean differences in peak creatinine (mg/dL) at the 2.5% significance level is given in Figure 5.

Figure 5. Power with 150 patients per group to detect various mean differences in creatinine (mg/dL) assuming normal distribution with various standard deviations at the two-sided 2.5% significance level

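### Sections 2.2 and 14.3 attach alpha 0.025 to different units, and 14.2 sets no level for the four primary tests; control 5% within each factor, using Holm.

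*Protocol*

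**What the plan says.** Sections 2.1 and 2.2 of the protocol set out four primary hypotheses: dose and route, each on 72-hour creatinine change and on the 72-hour AUC of the patient global assessment (PGA). Section 2.2 then closes with "Each factor (main effect) in the design will be tested at the α =0.025 level". It gives no derivation of that level.

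The only derivation is in section 14.3, where, for the power calculations, "we have applied a Bonferroni adjustment to the alpha level (0.05/2 = 0.025) to allow for two co-primary endpoints". Here the level belongs to the endpoints.

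Section 14.2 describes the analysis: "General linear models will be used to examine the effect of each of the main effects on the two co-primary outcomes". It gives no significance level for those tests. The 0.025 that appears in 14.2 governs only whether an interaction term is kept. The same section words the null hypothesis for a factor as no effect on either co-primary outcome.

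The power figures in 14.3.1 and 14.3.2 (88% for each endpoint) are calculated "at the two-sided 2.5% significance level". Section 14.1 adds a general default: "Statistical tests with a p value < 0.05 will be considered statistically significant, unless otherwise stated".

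**The concern.** The level is tied to the factor in one place and to the endpoint in another, and the section that defines the primary analysis does not say which applies. The two statements agree only if 0.025 is the level of a single factor-by-endpoint test. If 0.025 is taken as what a whole factor may spend, which is the literal sense of 2.2 and fits the joint null hypothesis in 14.2, the two endpoints must share it at 0.0125 each.

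This affects the primary result. A p-value of, say, 0.02 for dose on creatinine is positive under one reading and negative under the other. That choice should not still be open when the data are seen. An analysis plan could settle it, but it could be challenged against one section of the protocol whichever way it went.

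The plain Bonferroni split also gives up power that a better procedure would recover at the same error rate.

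**Working it through.** **Inputs.** 150 patients per level of each factor (Figure 5 caption, 14.3.1). Creatinine difference 0.20 mg/dL, SD 0.5 mg/dL (14.3.1). PGA AUC difference 600 points, SD 1500 points (14.3.2). Two endpoints (11.1) and two factors (14.2) give 2 × 2 = 4 primary tests.

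**Step 1: reproduce the stated power.** The standardised effect is 0.20/0.5 = 600/1500 = 0.4 for both endpoints. The noncentrality is 0.4/√(2/150) = 3.464. Normal approximation: power = Φ(3.464 − z), with z the two-sided critical value. The t column uses the noncentral t with 296 df.

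| Two-sided level per test | z | Power, normal | Power, t |
|---|---|---|---|
| 0.05 | 1.960 | 93.4% | 93.2% |
| 0.025 | 2.241 | 88.9% | 88.6% |
| 0.0125 | 2.498 | 83.3% | 82.8% |

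The protocol states 88%. Only the 0.025 row matches, so the design was powered with 0.025 for each factor-by-endpoint test.

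**Step 2: what each reading implies.**

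| Reading | Level per test | Error per factor, at most | Power per test (t) |
|---|---|---|---|
| 0.025 for each factor-by-endpoint test | 0.025 | 2 × 0.025 = 5% | 88.6% |
| 0.025 for a whole factor, split over two endpoints | 0.025/2 = 0.0125 | 2.5% | 82.8% |

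Under the second reading, 88% power needs 169 patients per level, about 338 in total (normal approximation). The readings disagree for any p-value between 0.0125 and 0.025.

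**Step 3: error over all four tests at 0.025.** The upper bound is 4 × 0.025 = 10%. If the tests are independent it is 1 − (1 − 0.025)⁴ = 9.6%. The correlation between the two endpoints is not given in the protocol. Assuming 0.3, 0.5, 0.7 or 0.9, with independent factor contrasts, the error is 9.5%, 9.1%, 8.4% or 7.1%.

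**Step 4: Bonferroni against Holm within one factor.** Holm compares the smaller of the two p-values with 0.025 and, if that is significant, the larger with 0.05. Error within the factor stays at or below 5%. Assume that both effects are present at the planned size and that the endpoints are independent. Take b = 0.8865 (power at 0.025) and a = 0.9323 (power at 0.05), both from the t calculation.

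- One given endpoint: Bonferroni b = 88.6%; Holm b + (a − b)·b = 0.8865 + 0.0458 × 0.8865 = 92.7%.
- Both endpoints: Bonferroni b² = 78.6%; Holm a² − (a − b)² = 0.8691 − 0.0021 = 86.7%.

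If only one effect is present, Holm's power for it is still at least b, because Holm rejects whatever Bonferroni rejects.

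**The case against.** The best defence is that the protocol already contains one coherent rule. The hypotheses before the sentence in 2.2 each name one factor and one endpoint. Section 14.3.1 powers creatinine for each main comparison, and 14.3.2 powers the PGA for each factor, at 2.5%. The null row of Table 1 shows 2.5% for the main-effect tests. No power calculation uses 0.0125. On this view 2.2 merely omits a mention of the endpoints. Most of this stands: 0.025 per factor-by-endpoint test is the likelier intention, and the power figures support it. But the reader has to infer it from the power section, because neither 2.2 nor 14.2 says so.

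Three stronger criticisms are tempting, and the protocol does not support them.

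- A reader might infer that 0.05 was halved once for the factors and again for the endpoints. Section 2.2 shows no halving. The only split is the one in 14.3, for the endpoints.
- A reader might infer that an error near 10% over four tests breaks the plan's own limit. No section promises 5% across both factors. Dose and route are presented as separate questions, and giving each factor of a factorial trial its own 5% is an accepted choice.
- A reader might infer that the 0.05 default in 14.1 could be claimed for the primary tests, giving 1 − (1 − 0.05)⁴ = 18.5%. That default yields wherever another level is stated, and 2.2 states one for the main effects.

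It can also be said that the detailed multiplicity procedure belongs in the analysis plan. That is fair for detail, but here the protocol itself fixes alpha, in two forms that do not match.

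**Conclusion.** The point holds as an ambiguity in the unit to which 0.025 applies, together with an improvement available at no cost in error. The 88% holds only if each factor-by-endpoint test is at two-sided 0.025. The literal whole-factor reading means 0.0125 per test and 83% power, a loss of about 6 percentage points (88.6% to 82.8%). Primary p-values from 0.0125 to 0.025 are open to dispute until the text is settled.

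The error of up to 10% over all four tests (9.6% if independent) follows from treating the factors separately. It should be disclosed and is not an error. Holding 5% over all four tests would be a trade-off that the sponsor may choose, not a correction that the protocol requires.

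The power figures rest on the protocol's own effect sizes and SDs, with no loss of patients. The Holm gains also assume independent endpoints and both effects present at the planned size. The gains change with correlation, but Holm's power never falls below Bonferroni's.

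**What to change.** 1. In 14.2, state that for each factor separately the family-wise error over the two co-primary endpoints is controlled at two-sided 5% by Holm's procedure: the smaller p-value is tested at 0.025 and, if significant, the other at 0.05. State that there is no adjustment across the two factors, and that the error over all four tests can therefore reach 10%.
2. Reword the closing sentence of 2.2 to refer to that rule, so that 0.025 no longer reads as the allowance for a whole factor.
3. In 14.3, say that power was calculated at two-sided 0.025 per test, which is Holm's first step, so 88% is the minimum power per endpoint.
4. In 14.1, say that the general 0.05 default does not apply to the primary tests.

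The cost is wording only; 300 patients and the 88% stand. Simultaneous confidence intervals that match Holm exactly are less simple than Bonferroni's, but 97.5% intervals for each endpoint remain valid and can be reported beside the tests. If the sponsor does want 5% over all four tests, a Bonferroni level of 0.05/4 = 0.0125 gives 83% power with 300 patients, and the stated power would have to be changed to match.

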2.3 Secondary Objectives

Other secondary objectives of this protocol will be to examine the effect of the above treatments on:

- Change in weight at 96 hours
- Freedom from signs and symptoms of congestion at 72 hours
- Change in bivariate vector of creatinine and weight at 72 hours
- Differences in Dyspnea VAS AUC over 24, 48 and 72 hours
- Differences in PGA VAS AUC over 24 and 48 hours
- Change in serum creatinine at 24, 48, 96 hrs, day 7 (or discharge), and day 60
- Change in cystatin C at 72 hours, day 7 (or discharge) and day 60
- Persistent or worsening heart failure
- Development of cardio-renal syndrome
- Treatment failure
- Time from randomization to discharge during index hospitalization
- Total days hospitalized for heart failure or dead within 60 days of randomization

DOSE protocol version 18.1; February 4, 2008

• Changes in circulating biomarkers from baseline to 72 hours, day 7 (or discharge), and day 60

3. BACKGROUND AND SIGNIFICANCE

Acute heart failure (AHF) is the most common cause of hospital admission in patients over age 65, accounting for 1,000,000 admissions, over 6 million hospital days, and \$12 billion in costs annually (1;2). The prognosis of patients admitted with AHF is dismal, with a 20-30% readmission rate and a 20-30% mortality rate within six months after admission (3;4).

IV furosemide is the most common treatment utilized in patients with AHF during the first days of admission in the United States (US) (5;6). In both previous studies and the recent ADHERE registry, approximately 90% of patients receive IV furosemide during an AHF admission. In the recent VERITAS study (unpublished data), 69% of patients in the US received IV furosemide at baseline (approximately 12 hours from admission) and 87% received IV furosemide during the study period (first 48 hours). This nearly ubiquitous use of loop diuretics in AHF is based on the concept that the majority of AHF symptoms are related to volume overload and congestion, and that loop diuretics are the most effective means to address symptoms and volume overload in AHF. Although these assumptions are based on years of clinical experience, data supporting the safety and efficacy of loop diuretics in AHF are sparse. Importantly, there is little data to guide appropriate dosing of loop diuretics during AHF therapy, and consequently practice varies widely between physicians and centers. Similarly, substantial uncertainty remains about the optimal route of administration (continuous infusion vs. intermittent bolus) for IV diuretics. In a recent publication on unanswered questions in heart failure management, over 50% of the questions related to use of loop diuretics in heart failure (7). In sum, almost all patients with AHF are treated with a therapy (IV loop diuretics) about which there is substantial uncertainty regarding the correct dose and route of administration, both in terms of efficacy and safety. In light of these uncertainties, the overriding goal of this clinical protocol is to evaluate the safety and efficacy of various strategies of intravenous loop diuretics in patients presenting with AHF and volume overload.

4. PRELIMINARY STUDIES

4.1 Safety of Loop Diuretics: Relationship to Mortality

As noted above, the use of loop diuretics is nearly universal in patients with AHF (5). A variety of theoretical considerations suggest potential mechanisms of harm from loop diuretics in heart failure, including activation of the renin-angiotensin-aldosterone system, activation of the sympathetic nervous system, and the induction of vasoconstriction or hypotension. A large body of literature supports the concept of higher mortality in patients receiving higher doses of loop diuretics (6;8;9). In an analysis of the recently completed ESCAPE trial (unpublished data), there was a direct relationship identified between dose of loop diuretics and increased mortality (Figure 1).

and mortality in ESCAPE study.

Confounding this and all other such data is the issue of confounding by indication, i.e., the fact that patients who receive higher doses of diuretics may do so because of greater disease severity compared to patients who can be successfully treated with lower doses of diuretics. Although such confounding can never be completely eliminated, a variety of studies have found a persistent adverse effect of loop diuretics even after multi-variable adjustment for other known predictors of mortality (9;10). In further analyses of data from the ESCAPE trial, total diuretic dose was not clearly linked to other measures of disease severity such as levels of B-type natriuretic peptide (BNP) or to measures of volume overload such as pulmonary capillary wedge pressure (Figure 2). Although such data do not eliminate the problem of confounding by indication, they suggest that dosing of diuretics is not closely linked to other measures of disease severity. Taken as a whole, the available data clearly suggest the presence of a dose related mortality signal with increasing doses of loop diuretic therapy in AHF.

Figure 2. Pulmonary capillary wedge pressure versus maximum in-hospital furosemide dose in ESCAPE.

4.2 Safety of Loop Diuretics: Relationship to Renal Function

Worsening of renal function during hospitalization for AHF (termed the "cardio-renal syndrome" (CRS)) is a major clinical challenge in AHF management. It is well established that development of CRS during AHF therapy is a major risk factor for increased length of stay, higher morbidity, and greater mortality (10;11). Although a variety of mechanisms have been proposed for CRS, the pathophysiology of this syndrome has not been clearly elucidated (12). Butler et al examined the factors contributing to the development of renal failure in a cohort of patients admitted with AHF, and identified an association between higher doses of loop diuretics and the development of CRS during AHF therapy (9). This relationship persisted even after adjustment for baseline renal function and a variety of other covariates. As with the mortality data, these observational associations regarding loop diuretics and the CRS are highly confounded by indication, and can only be definitively addressed by a well controlled randomized controlled trial. A preliminary small study examining the role of high-dose furosemide, low-dose dopamine and their combination in patients with AHF was terminated early due to increased renal impairment and renal failure in the high dose furosemide arms (13).

